#### **6.5.1 Rescue medicine**

All participants on 1- to 3-fold the approved non-sedating H1-AH dose (maintenance dose used at screening) will be allowed to take additional doses of their H1-AH medications as rescue therapy as long as they do not exceed 4-fold the recommended dose during the screening, treatment, and follow-up periods. If symptoms are still uncontrolled after increase of H1-AH to the maximum allowed dose, participants can take a short course of OCS as rescue therapy during the treatment and follow-up periods. The participants on stable dose of 4-fold the approved H1-AH dose will be allowed to take a short course of OCS as rescue therapy during the treatment and follow-up periods. In order to ensure consistency, when possible, it is recommended to use OCS for 5 to 7 days with a starting dose of oral prednisone 40 mg (or clinically comparable OCS) followed by taper per the Investigator's judgment.

For rescue medication in participants in Japan, please see Appendix 11 ([Section 10.11](#)).

The initial maintenance antihistamine dose should remain stable throughout the study, and participants should continue their maintenance dose once rescue treatment is no longer required.

The use of permitted rescue medications should be delayed, if possible, for at least 8 weeks following the initiation of the investigational treatment. The date and time of rescue medication administration as well as the name and dosage regimen of the rescue medication must be recorded.

For other information related to H1-AH and OCS including safety precautions please refer to the National Product labeling.

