| | Change from baseline in UAS7 at Week 24 (EU and EU reference countries) | | 
 Discontinuing the study intervention (but not taking selected prohibited and/or rescue medications^b prior to Week 24): all data collected after discontinuation will be used in the analysis (treatment policy strategy). Taking selected prohibited medications and/or rescue medications^b prior to Week 24: data will be excluded after the medication usage, and the participant's worst post-baseline value on or before the time of the medication usage will be assigned to the Week 24 value (for participants whose post-baseline values are all missing, the participant's baseline value will be used for the Week 24 value) (composite strategy) 
After applying the rules for intercurrent events, if there is still missing data, then the missing data imputation rules are as follows:
 
 After study intervention discontinuation due to lack of efficacy prior to Week 24: WOCF approach (as described above) will be used to impute missing data if needed. After study intervention discontinuation due to reasons other than lack of efficacy prior to Week 24: multiple imputation (MI) approach will be used to impute missing Week 24 value, and this multiple imputation will use all participants excluding participants who have taken the selected prohibited medications and/or rescue medications prior to Week 24 and excluding participants who discontinue study intervention due to lack of efficacy prior to Week 24. | | |

| Endpoint Category | Estimands | | | |
|---|---|------------|---|---|
| | Endpoint(s) ^a | Population | Intercurrent event(s) handling strategy and missing data handling | Population-level summary |
| Secondary objective: To demonstrate the efficacy of dupilumab on urticaria activity composite endpoint and itch or hives, separately, at various time points | | | | |

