4.3 PRIMARY ENDPOINT(S) ANALYSIS

4.3.1 Definition of endpoint(s)

The primary efficacy endpoint is the change from baseline in ISS7 at Week 24.

For EU and EU reference countries, the primary efficacy endpoint is the change from baseline in UAS7 at Week 24.

The once daily UAS is the sum of the daily HSS (ranging from 0 = None to 3 = more than 50 hives) and the daily ISS (ranging from 0 = None to 3 = intense), assessing the 2 key urticaria signs and symptoms which are wheals and itch. The daily UAS scores range from 0 to 6 point/day. The daily UAS scores are summed over 7-day period to create the UAS7, ranging from 0 to 42, and is composed of the HSS7 and ISS7 components.

For daily e-diary endpoints, the baseline values are the sum of the 7 measurements obtained within the 7 days prior to randomization. Note: To be eligible for the study, participants must have no missing e-diary (UAS7 and ISS7) entries in the 7 days prior to randomization.

For the Week 24 score, the sum of the 7 days on and prior to the target visit day will be used (ie, sum of days 163 through 169). If there are less than 7 but at least 4 non-missing scores available, the weekly score is the sum of the available scores in the 7 days, divided by the number of days that have a non-missing score, multiplied by 7. If there are less than 4 non-missing scores, the weekly score is missing. This same rule will be applied for other weekly scores.

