The primary efficacy endpoints will be analyzed using an analysis of covariance (ANCOVA) model with the baseline value of the primary endpoint, intervention group, presence of angioedema at baseline, and region as covariates, with intercurrent events and missing data being handled by a hybrid method of the worst-observation carried forward (WOCF) and multiple imputation. For participants taking selected prohibited medications and/or rescue medications (see [Table 4](#)), their data after the medication start date will be excluded, and the worst postbaseline value on or before the time of the medication usage will be assigned to the Week 24 value (for participants whose postbaseline values are all missing, the baseline will be used). Participants who discontinue the intervention prematurely are encouraged to follow the planned clinical visits and in these participants who did not take the selected prohibited medications and/or rescue medications, all data collected after intervention discontinuation will be used in the analysis. For these participants, missing data may still happen despite all efforts to collect the data after intervention discontinuation. For participants who discontinue study intervention due to lack of efficacy, all data collected after discontinuation will be used in the analysis, and a WOCF approach will be used to impute missing Week 24 value if needed (ie due to study discontinuation). For participants who discontinued study intervention for reasons other than lack of efficacy, a multiple imputation approach will be used to impute the missing Week 24 value. This multiple imputation will include all participants except participants who have taken the selected prohibited medications and/or rescue medications on or before Week 24 and will also exclude participants who discontinued study intervention due to lack of efficacy on or before Week 24.

Each of the imputed complete data will be analyzed by fitting an ANCOVA model as described above. Statistical inference obtained from all imputed data will be combined using Rubin's rule. Descriptive statistics including number of participants, mean, standard error, and least squares (LS) mean changes (and standard error) score will be provided. In addition, difference of the dupilumab group against placebo in LS means and the corresponding 95% confidence intervals (CI) will be provided along with the p-values.

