5.5 APPENDIX 5 SAMPLE SAS CODE

The multiple imputation and analysis model for the primary analysis approach will be built with the following sample SAS code.

1. 40 datasets with a monotone missing pattern will be obtained, induced by Markov Chain Monte Carlo (MCMC) method on participants who have not taken selected prohibited medications and/or rescue medications or have not discontinued study intervention due to lack of efficacy prior to Week 24.

A large rectangular area of the page is completely blacked out, representing a redaction of the SAS code for the first step.

2. For each of the imputed dataset with monotone missing pattern in step 1, the remaining missing data will be imputed using the regression method for the monotone pattern with adjustment for covariates including intervention groups, region, angioedema status at baseline and baseline value of the response variable.

[figure not shown]
A large rectangular area of the page is completely blacked out, representing a redaction of the SAS code for the second step.

3. Each of the 40 imputed datasets will be merged with the one dataset imputed by WOCF approach, and then be analyzed using the main statistical model. These 40 imputed datasets will be saved.

A large rectangular area of the page is completely blacked out, representing a redaction of the SAS code for the third step.

4. Applying Rubin's rule to combine analysis results (point estimates and standard errors) from 40 imputations using PROC MIANALYZE for the LS means and difference in LS means between dupilumab and placebo. Sample code:

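### The Study C SAP gives the primary rescue rule different end dates in different places, and Section 4.3.2 as written lets a first rescue course in follow-up replace an observed Week 24 score

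*SAP*

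**What the plan says.** The Study C SAP states or uses the rescue rule for the primary endpoint in several places.

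- **Section 1.2.1, Table 2 (estimand).** The composite rule covers selected medications taken "prior to Week 24: data will be excluded after the medication usage". The table uses the same limit for leaving participants out of the multiple imputation (MI) model.
- **Section 4.3.2, assignment of the value.** For participants taking these medications, the instruction reads "their data after the medication start date will be excluded, and the worst postbaseline value on or before the time of the medication usage"; that worst score then stands as the Week 24 result, with baseline substituted when no post-baseline score exists. The sentence has no end date and does not require the Week 24 value to be missing.
- **Section 4.3.2, MI pool.** Participants are left out if they have taken "selected prohibited medications and/or rescue medications on or before Week 24".
- **Section 4.3.4, worst-possible-score analysis.** A score of 21 (ISS7) or 42 (UAS7) is assigned to Week 24 after a selected medication, again without an end date.
- **Appendix 5, step 1.** The MI uses participants who have not taken the selected medications or "have not discontinued study intervention due to lack of efficacy prior to Week 24".

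Week 24 itself has two uses. In Section 4.3.1 the score is the "sum of days 163 through 169". Section 4.4.2 equates Week 24 with Day 169, and the Appendix 4 tables give Day 169 as the target day.

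Protocol Section 6.5.1 states that "participants can take a short course of OCS as rescue therapy during the treatment and follow-up periods". Study C SAP Section 4.9 places the primary lock after all participants have finished 24 weeks and analyses everything collected by then. The protocol (synopsis and Section 9.4.1, Table 7) and the Study A and Study B SAPs (Section 4.3.2 of each) use the worst value only to fill in a missing Week 24 score.

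**The concern.** This rule decides who is a treatment failure in the primary endpoint and which participants inform the imputation. If its end date varies by section, one participant can have two primary values depending on which section the programmer follows.

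The more serious case is follow-up. A participant may complete Week 24 without rescue, have an observed score, and take a first OCS course some weeks later. Because the lock waits for the last participant, earlier participants' follow-up records will be in the data. Under the literal 4.3.2 sentence, that course causes the worst value up to its start date to be assigned to Week 24, including diary weeks after Week 24.

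The second case is a start at the Week 24 boundary, where Table 2 and Section 4.3.2 disagree. If either is settled after unblinding, the choice can be questioned.

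**Working it through.** **1. The plan's own figure.** Protocol Section 9.2 gives an ISS7 difference of 4.23, an SD of 7.5, two-sided alpha 0.05, 90% power and 10% dropout. The effect size is 4.23 / 7.5 = 0.564. This needs 67 per group (exact t-test power 0.900), and 67 / 0.90 = 74.4, so 75 per group. The stated figure is reproduced and is not in dispute. It supplies the scale for step 4.

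**2. Each wording applied to one participant.** Assumed values: baseline ISS7 16, worst value before Week 24 of 15, observed Week 24 score 6, worst value up to Day 211 of 17. The possible changes from baseline are 15 − 16 = −1, 6 − 16 = −10 and 17 − 16 = +1.

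| First selected medication | Table 2, Week 24 = Day 169 | Table 2, Week 24 = Days 163–169 | Section 4.3.2 as written | Start on or before Day 169 |
|---|---|---|---|---|
| Day 160 | −1 | −1 | −1 | −1 |
| Day 165 | −1 | −10 | −1 | −1 |
| Day 168 | −1 | −10 | −1 | −1 |
| Day 169 | −10 | −10 | −1 | −1 |
| Day 211 (follow-up) | −10 | −10 | +1 | −10 |

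Table 2 and Section 4.3.2 disagree for a Day 169 start and for a follow-up start on either meaning of Week 24. For Days 163–168 they disagree only if Week 24 means the diary window.

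**3. The MI pool.** The Section 4.3.2 limit on the pool does not set a rescued participant's value, so it does not produce the differences above. It matters if sections are mixed. With Table 2 deciding who receives the worst value and 4.3.2 deciding the pool, a Day 169 starter belongs to neither set.

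**4. Size.** The documents give no rescue rates and no gap between worst and observed scores, so both are assumptions.

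- Suppose 5% to 20% of 150 participants start a selected medication by Day 169, evenly over 16 to 24 weeks. Starts in Days 163–169 number 150 × 0.05 / 24 = 0.3 to 150 × 0.20 / 16 = 1.9, both arms together. For Day 169 alone, dividing by 7 gives about 0.04 to 0.27.
- For a gap of 5 to 12 ISS7 points, one reclassified participant moves an arm mean by 5 / 75 = 0.07 to 12 / 75 = 0.16, which is 2% to 4% of 4.23.
- The unadjusted standard error of the difference is 7.5 × √(2/75) = 1.22. One participant's shift is 5% to 13% of it.
- If four participants in one arm had a first follow-up course, the literal 4.3.2 reading would move that arm's mean by 4 × 5 / 75 = 0.27 to 4 × 12 / 75 = 0.64. The number four is illustrative.

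**The case against.** The strongest reply is that, read as a whole, the SAP is not ambiguous.

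- Table 2 defines the estimand and sets a limit. Section 1.2.1 says Section 4 adds detail, not that it replaces the table.
- Section 4.3.2 justifies the rule by the medications' possible effect on efficacy. A course begun after Day 169 cannot affect a score from Days 163–169.
- The protocol restricts the worst value to a missing Week 24 score, and the SAP's version history reports no major departure from the protocol.
- The responder rule in Section 4.4.2 is limited to time points after the medication.
- The as-observed and worst-possible-score analyses already examine rescue handling.

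Much of this stands. It shows that keeping the observed score is the better-supported reading, and a careful programmer would probably do so. It does not remove the literal instruction in 4.3.2, which assigns a value without an end date and has lost the condition that bounded it in the protocol and the two earlier SAPs. The worst-possible-score analysis has the same undated assignment, so it is no independent check.

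Two stronger readings are not supported. A reader might infer that any start in Days 163–169 falls outside Table 2, so that steroid-treated diary days always count. That requires Week 24 to mean the diary window, whereas Section 4.4.2 and the target days point to Day 169. A reader might also infer that the contrast between the Table 2 limit and the MI-pool limit itself creates two primary values. It does not, because the pool limit governs only who informs the imputation.

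**Conclusion.** The inconsistency is real and can change individual primary values. Section 4.3.2, followed literally, gives a value that conflicts with Table 2 and the protocol when a first rescue course falls in follow-up. A Day 169 start is also handled differently in the two sections. For Days 163–168 the conflict is conditional on reading Week 24 as the diary window.

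The effect on the trial result is probably small. At the boundary, well under one participant is expected on Day 169 under the assumed rates. The follow-up effect cannot be estimated, because the number of first courses before lock is unknown. For the same reason no direction of bias between arms can be claimed. The sample size is unaffected. This is a minor correction to make before lock, not a threat to the design.

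**What to change.** State one rule and use it in Table 2, Sections 4.3.2 and 4.3.4, and Appendix 5:

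- The intercurrent event is a selected medication, confirmed by the blinded medical review, with a start date on or before Day 169 (Day 85 for Week 12 endpoints).
- The same date limit defines who is left out of the MI pool for rescue.
- A later start does not alter the Week 24 value.

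The cost is one phrase in each of these places and one date condition in the program before database lock. It needs no new data and leaves the rescue provisions for participants unchanged.

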2 SAMPLE SIZE DETERMINATION

For Study C (omalizumab naive): Assumptions for sample size calculations for Study C were based on Study A results. An effect size of 0.564 or higher is assumed. Based upon an SD of 7.5 (pooled SD from the observed data in Study A), a treatment difference of [REDACTED] in the ISS7 would correspond to an effect size of approximately [REDACTED]. Based upon an SD of [REDACTED] (pooled SD from the observed data in Study A), a treatment difference of [REDACTED] in the UAS7 would correspond to an effect size of approximately [REDACTED]. Based on this assumption, plus the assumption of a 10% dropout rate, it is estimated that 75 participants per group will provide 90% power to detect an effect size of [REDACTED] or higher between the dupilumab arm and placebo using a 2-sided t-test with alpha = [REDACTED]. This sample size estimate applies to both ISS7 and UAS7 (primary endpoint for EU and EU reference countries).

The sample size calculations were calculated by nQuery Advisor and nTerim 4.0.

3 ANALYSIS POPULATIONS

The following populations for analyses are defined:

Table 3 - Populations for analyses

| Population | Description |
|-------------------------|--|
| Screened | All participants who sign the ICF |
| Randomized | All participants from the screened population who have been allocated to a randomized intervention by IRT regardless of whether the treatment kit was used or not. Participants treated without being randomized will not be considered randomized and will not be included in any efficacy population. |
| Intent-to-treat (ITT) | All randomized participants analyzed according to the intervention group allocated by randomization. |
| Safety | All participants randomly assigned to study intervention and who take at least 1 dose of study intervention. Participants will be analyzed according to the intervention they actually received. Randomized participants for whom it is unclear whether they took the study medication will be included in the safety population as randomized. For participants who accidentally receive a different intervention from that which was planned, the actual intervention allocation for as-treated analysis will be the dupilumab group. The pharmacodynamic (PD) analyses will be performed on the safety population. |
| Pharmacokinetic (PK) | The PK population includes all participants in the safety population with at least one non-missing result for functional dupilumab concentration in serum after first dose of the study intervention. Participants will be analyzed according to the intervention actually received. |
| Antidrug antibody (ADA) | ADA population includes all participants in the safety population who have at least one non-missing ADA result after first dose of the study intervention. Participants will be analyzed according to the intervention actually received. |

Abbreviations: ADA = antidrug antibody; ICF = Informed consent form, IRT = Interactive response technology; PD = Pharmacodynamic

Participants exposed to study intervention without being randomized will not be considered randomized and will not be included in any analysis population. The safety experience of these participants will be reported separately.

Randomized participants for whom it is unclear whether they took the study intervention will be considered exposed and will be included in the safety population as randomized.

For any participant randomized more than once, only the data associated with the first randomization will be used in any analysis population. The safety experience associated with any later randomization will be reported separately.

For participants receiving more than one study intervention (placebo and dupilumab) during the study, the intervention group for as-treated analysis will be the dupilumab group.

If >10% of participants are impacted by the COVID-19 pandemic, additional summaries by COVID-19 subgroups will be provided. Participants impacted by the COVID-19 pandemic are defined as randomized participants with any critical or major deviation related to COVID-19 or who permanently discontinued study intervention or study due to the COVID-19 pandemic.

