**Table 6 - Populations for analyses**

Population	Description
Screened	All participants who sign the ICF
Randomized	The randomized population includes all participants with a treatment kit number allocated and recorded in the IRT database, and regardless of whether the treatment kit was used or not.  Participants treated without being randomized will not be considered randomized and will not be included in any efficacy population.
Intent-to-treat (ITT)	All randomized participants analyzed according to the treatment group allocated by randomization.

Population	Description
Intent-to-treat24 (ITT24) (For Study B interim analysis)	All participants who were randomized at least 24 weeks before the interim analysis cut-off date and would have completed the Week 24 visit by the cut-off date of interim analysis. The exact interim analysis cut-off date will be specified in the SAP, which will be finalized before the interim analysis.
Efficacy	The ITT population (ITT24 for Study B interim analysis).
Safety	All participants randomly assigned to study intervention and who take at least 1 dose of study intervention. Participants will be analyzed according to the intervention they actually received.  Randomized participants for whom it is unclear whether they took the study medication will be included in the safety population as randomized.  For participants who accidentally receive different treatment from the planned, the actual intervention allocation for as-treated analysis will be the dupilumab group.  The pharmacodynamic (PD) analyses will be performed on the safety population.
Pharmacokinetic (PK)	The PK population includes all participants in the safety population with at least one non-missing result for functional dupilumab concentration in serum after first dose of the study treatment. Participants will be analyzed according to the intervention actually received.
Antidrug antibody (ADA)	ADA population includes all participants in the safety population who have at least one non-missing ADA result after first dose of the study treatment. Participants will be analyzed according to the intervention actually received.

Abbreviations: ADA = antidrug antibody; ICF = Informed consent form, IRT = Interactive response technology; PD = Pharmacodynamic

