4.7 SAFETY ANALYSES

All safety analyses will be performed on the safety population as defined in [Section 3](#), unless otherwise specified, using the following common rules:

- The analysis of the safety variables will be essentially descriptive, and no testing is planned.
- Safety data in participants who do not belong to the safety population (eg, exposed but not randomized) will be provided separately.

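### The Safety-row rule for accidental misallocation counts a participant randomized to dupilumab who received only placebo as dupilumab, against the as-received rule in the same cell.

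*SAP*

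**What the plan says.** The Safety row of Table 3 (Study C SAP, section 3) contains two grouping rules. The first is the as-received rule: "Participants will be analyzed according to the intervention they actually received". The second applies to dispensing errors, whichever way they run: anyone accidentally given something other than the planned intervention is covered. Its outcome is that "the actual intervention allocation for as-treated analysis will be the dupilumab group".

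Below the table is a rule for mixed exposure. Its scope is stated as "For participants receiving more than one study intervention (placebo and dupilumab) during the study", and it counts these people as dupilumab.

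The PK and ADA rows of the same table use the as-received rule with no exception.

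Protocol section 9.3, Table 6, has the same pair of rules in its Safety row, with the error rule introduced by "For participants who accidentally receive different treatment from the planned". It has no mixed-exposure rule. Table 4 of the Study A SAP and Table 4 of the Study B SAP repeat the sentence, each with a mixed-exposure rule below the table.

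On scope, section 4.7 of the Study C SAP states: "All safety analyses will be performed on the safety population as defined in" section 3. Table 3 places the pharmacodynamic analyses on that population too, and section 4.8.3 summarizes total IgE in it by intervention group.

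**The concern.** The error rule is triggered by a mistake in either direction, yet it has one outcome, dupilumab, and no condition that any dupilumab was received. Taken as written, it classes as dupilumab a person who was never exposed to the drug, while the as-received rule in the same cell classes that person as placebo.

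Two things are at stake. First, an unexposed participant would stay in the dupilumab denominator for adverse events, laboratory results and IgE. Second, groupings would differ between tables: the same person would be dupilumab in the adverse-event and IgE outputs and placebo in the PK and ADA outputs. The exploratory look at safety by ADA status (section 4.8.2.1), which uses the ADA population, would then not match the main safety tables. If such a case arose, someone would have to choose between two written rules after the fact.

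**Working it through.** The plan gives no figure to reproduce. The check applies each rule to each kind of misallocation.

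| Randomized to | Received | As-received rule | Error rule | Mixed-exposure rule | Conflict? |
|---|---|---|---|---|---|
| Placebo | Dupilumab only | Dupilumab | Dupilumab | Does not apply | No |
| Either arm | Both products | Does not settle it | Dupilumab | Dupilumab | No |
| Dupilumab | Placebo only | Placebo | Dupilumab | Does not apply | **Yes** |

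In the first row the error rule adds nothing to the as-received rule. In the second it duplicates the mixed-exposure rule of the SAP. It changes the result only in the third row, and there the result is wrong. The mixed-exposure rule cannot correct it, because that rule is confined to participants who received both products.

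**Size.** The only input is the planned arm size, from Study C SAP section 2: "it is estimated that 75 participants per group will provide 90% power". The documents give no count of misallocations.

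- One case: 1/75 = 1.3% of the dupilumab safety denominator.
- An assumed range of 1 to 3 cases: 1/75 = 1.3% to 3/75 = 4.0%.

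This participant was randomized to dupilumab, so is already among the 75. With one case, the dupilumab safety group is reported as 75 when it should be 74, and placebo as 75 when it should be 76.

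**Direction.** Let p_D and p_P be the event rates on dupilumab and placebo, and suppose the placebo-only participant has the placebo rate. With one case in 75, the expected reported dupilumab rate is (74 × p_D + p_P)/75. It differs from p_D by (p_P − p_D)/75. The Study A rates come from protocol section 2.1.

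- Any treatment-emergent adverse event, 58.8% on placebo and 54.3% on dupilumab: (58.8 − 54.3)/75 = +0.06 percentage points.
- Angioedema, 7.4% and 1.4%: (7.4 − 1.4)/75 = +0.08 percentage points.
- A reaction that occurs only on the drug (p_P = 0): the reported rate is 74/75 of the true rate, a relative reduction of 1.3%.

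So the error dilutes drug-specific reactions, such as the injection site reactions and conjunctivitis listed as adverse drug reactions in protocol section 2.3. It slightly raises the reported rate of events that are more frequent on placebo.

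**The case against.** The strongest reply is that the intent is plain and the case hardly arises. The cell opens with the as-received rule, the PK and ADA rows repeat it, and the SAP says separately when dupilumab takes precedence. An adult course is 13 syringes: two on Day 1, then one every two weeks from Week 2 to Week 22, which is 11 more. Each is packed as its own kit and allocated centrally. Placebo-only exposure in the dupilumab arm needs every kit to be wrong, or a wrong first dose followed by early stopping. One wrong kit in an otherwise correct course gives mixed exposure, where the SAP's rules agree. Safety analyses are descriptive, and efficacy is analysed as randomized.

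Most of this stands: the sentence is probably a drafting slip, and its effect is small. It does not remove the conflict. A programmer works from the written rule, and the protocol does not even have the mixed-exposure sentence from which to infer the intent.

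A reader might infer two stronger things, and the documents support neither. One is that the rule flatters the drug's safety profile in general. Study A had more adverse events overall on placebo, so for that summary the expected error runs the other way. The other is that the plan deliberately moves misallocated participants into the dupilumab group. In the other misallocation cases dupilumab is the correct or conventional group.

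**Conclusion.** The rule is wrong as written, in one case: randomized to dupilumab, received only placebo. Each occurrence keeps one unexposed participant in the dupilumab safety group, about 1.3% of it, assuming 75 treated per arm. How many cases occur is unknown, and none is a realistic possibility. The effect is confined to the safety and PD summaries and their agreement with the PK and ADA outputs. The direction depends on the event: dilution for drug-specific reactions, possibly a slight increase for events more common on placebo. The figures for the latter assume that Study C resembles Study A. This is a minor point, worth correcting because the correction is nearly free.

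**What to change.** In Table 3 of the Study C SAP, limit the error sentence to participants who received at least one dose of dupilumab, and state that participants who received only placebo are analysed as placebo. Deleting the sentence would also work, since the as-received rule and the mixed-exposure rule together cover all three cases. Align protocol section 9.3, or note in the SAP that it is to be read this way. The cost is one sentence, with no new data or analysis, and it should be settled before database lock.

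Do not rewrite the SAPs for Studies A and B. Study A is complete with results reported, and Study B met its futility criterion at the interim analysis. For those studies, confirm from the dosing records that no dupilumab-randomized participant received only placebo, and use the corrected rule in any pooled safety analysis, which section 4.1 of both SAPs leaves open.
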